## 1. Abbreviations and Definitions

Term	Definition
BOTOX	Botulinum toxin
CRF	Case Report Form
DCF	Data Clarification Form
EMG	Electromyography
IIQ-7	Incontinence Impact Questionnaire – Short Form
I-QOL	Incontinence Quality of Life
ISF	Investigator Site File
OAB	Overactive Bladder
OAB-q	Overactive Bladder questionnaire
OHQ	Oxford Happiness Questionnaire
PGIC	Patient's Global Impression of Change
PTNS	Percutaneous Tibial Nerve Stimulation
SAE	Serious Adverse Event
SNS	Sacral Nerve Stimulation
UII	Urge Urinary Incontinence
WiFi	Wireless Fidelity

## 2. Protocol Summary

Title	A prospective efficacy study comparing frequency of use and efficacy of a surgery-free wearable personalized bladder modulation system with objective confirmation of nerve activation for use in the home by subjects with Overactive Bladder syndrome.
Test Article	Avation Medical's surgery-free wearable and personalized bladder modulation system that provides objective confirmation of nerve activation, can be used in a home environment, and is controlled with a tablet-based application
Protocol Number	AMHOAB2001
Objectives	
 
• To compare the effectiveness of 1 treatment session per week to 3 treatment sessions per week on OAB symptoms using the Test Article.
 
• To evaluate the overall effectiveness.
 
• To evaluate any side effects of the Test Article.
 
• To evaluate the tolerability, usability, and satisfaction of the Test Article.
 
• To evaluate the compliance of subjects using the Test Article.
 

Subject Population	Subjects diagnosed with OAB.
Population Size	80 completed subjects
Number of Centers	Up to 12 sites
Structure	Prospective open label study, 12-week treatment duration with an optional additional 21-month long-term follow-up period, for a total participation time of 24 months.
Method of Assignment	All subjects who meet the inclusion/exclusion criteria and sign the informed consent will be enrolled. Subjects will be randomized to once a week or three times a week of stimulation for a twelve-week period. Eligible subjects that elect to enroll in the long-term follow up study will sign a new informed consent and then be instructed to slowly taper down their treatment frequency stepwise from three treatment sessions per week, to two per week, to one per week, and finally one session every other week. The subjects that were assigned to one treatment session per week in the lead-in portion of the study will move directly to twice monthly treatment sessions. Subjects will then be instructed to perform treatments as needed or a minimum of twice per month.

Randomization	1:1, 1 treatment session per week: 3 treatment sessions per week
Selection Criteria	
Inclusion Criteria: To be eligible for study entry, subjects must satisfy all of the following inclusion criteria:
 
 
1. Male or female and 18 years of age or older at the time of enrollment
 
2. Willing and capable of giving informed consent
 
3. Willing and able to comply with study-related requirements and procedures
 
4. Are an appropriate candidate for the study Test Article based on the clinical judgment of the Investigator.
 
5. Have been diagnosed or have symptoms of OAB for at least 3 months prior to enrollment
 
6. Have an average of 10 or more frequency events per day in a 3-Day Bladder Diary
 
7. Able to provide clear, thoughtful responses to questions and questionnaires
 
8. Able to toilet self and have and maintain personal hygiene
 
9. Able to don and doff the bladder modulation garment on their ankle area, replace Gel Pads and use the controller
 
10. Have ankle and foot anatomy that allows the garment to fit properly, including having the hook and loop closures close and without excessive gapping and allowing the electrodes to fit firmly on the skin.
 
11. Able to sense and tolerate stimulation for the entire 30-minute therapy session
 
12. Has detectable EMG signal in response to modulation system stimulation during an investigator supervised screening session
 
13. If currently on medications that may affect their OAB symptoms, is on a stable dose (no new, discontinued, or change in dose) of all prescribed medication for at least 4 weeks prior to enrollment
 
14. Female subjects of child-bearing potential must have a negative urine dip stick pregnancy test at baseline
 
15. Have access to Wi-Fi at least weekly
 
16. Are capable of using the tablet-based controlling app
 

**Exclusion Criteria:** Subjects will be excluded from the study if 1 or more of the following exclusion criteria are applicable:

1. Have evidence of an active disruptive psychological or psychiatric disorder or other known condition significant enough to impact perception of pain, compliance of intervention and/or ability to evaluate treatment outcomes, in the opinion of the investigator.
2. Allergic, or have shown hypersensitivity, to any materials of the system which come into contact with the body
3. Have a pacemaker or implanted defibrillator
4. Have a documented current or reoccurring Urinary Tract Infection (3 or more in the 12months prior to enrollment)
5. Current use of a marketed device for treatment of their OAB or incontinence (including but not limited to Interstim®)
6. Have had Botox treatment for their OAB in the previous 8 months
7. Current use of TENS in pelvic region, back or legs
8. Had PTNS treatment within 6 months prior to enrollment
9. Use of investigational drug/device therapy within past 12 weeks
10. Current participation in another clinical study
11. Had within 6 months of enrollment a significant untreated substance abuse disorder or polysubstance abuse disorder stemming from dependency producing medications, alcohol, and/or illicit drugs
12. Pregnant or planning to become pregnant within the next 12 weeks
13. Has scar tissue, metal, or other implant in the target ankle that would interfere with stimulation
14. Has a neurological disorder that causes abnormal sensations in the lower leg (loss of sensation or allodynia)
15. Has a neurological disorder that affects the bladder or a diagnosis of interstitial cystitis, radiation cystitis, or fistulas.
16. Has a skin condition in the area of the ankle stimulation location that would preclude them from using surface stimulation
17. Has been diagnosed with incontinence due to neurogenic bladder
18. Have failed a third line treatment for their OAB because of lack of effectiveness in the last 2 years (PTNS, Botox, or SNS)
19. Urge incontinence due to stress predominant mixed urinary incontinence (greater than 60% of the time)
20. Have polyuria (>2500 cc urine output per day)
21. Has urinary retention or incomplete bladder emptying
22. Has symptoms of benign prostatic hyperplasia (weak stream, straining, hesitancy, or intermittency)

Study design	
Subjects that have signed the Informed Consent Form and meet all applicable eligibility criteria will be randomized 1:1 to 30-minute stimulation treatments either once a week or three times a week over a treatment period of 12 weeks.
 
Subjects will return to the clinic at 1-, 4-, 8-, and 12-weeks post-baseline for visit assessments listed in the Schedule of Activities. Investigative sites may elect to have some visits completed remotely via use of ePRO for visit questionnaires. On weeks where a subject does not have an in-clinic visit, they will be contacted by phone and queried for health and medication changes and any device issues. At the end of the first 12 weeks of stimulation, subjects will return to the clinic for final assessments, then will either enroll in the long-term follow up phase, if eligible, or exit from the study.

Statistical Methods	
Analyses will be performed within both the intent-to-treat (ITT) population of all enrolled patients and among the subset of patients who complete the study. Patients may be missing endpoint data at one or more, or possibly all, post-screening time points, at which endpoint data will be provided by carrying forward the most recent observation. Enrollment will continue until 80 patients complete the study. Expecting 15% dropout, the anticipated total enrollment will be approximately 94 patients.

### 3. Introduction

Overactive bladder is a stressful and disruptive chronic disorder that affects more than 16% of the adult population [1], an estimated 42 million adults in the just the United States alone. The symptoms of OAB cause millions of individuals to suffer with a decrease in their quality of life and put them at increased risk of falls, bone fractures due to falls and higher rates of anxiety and depression

OAB is characterized by four symptoms; urgency, frequency, nocturia, and urge incontinence[2]. Urgency is the complaint of a sudden, irresistible desire to pass urine which often is difficult to resist. Frequency is the number of voids per day. In OAB, there are usually 8 or more voiding episodes during waking hours. Nocturia is the number of voids per night. In OAB, the complaint of sleep interruption due to the need to void is 1+ times, per night. Urge incontinence is the involuntary leakage of urine, associated with sudden compelling desire to void. In order to be diagnosed, these symptoms or a combination of them, must be present without a pathologic or metabolic component causing them[3].

According to the American Urological Association, the first line of treatment is behavioral therapy. These therapies include the use of exercises, timed voiding, and fluid monitoring. This approach may be effective for some, but many patients are not compliant, and they do not see consistent relief of symptoms [2]. The next line of treatment is medications. Medication can be effective in around 70% of patients but they can produce significant side effects and are cost prohibitive[4]. Further, more than 70% of patients quit drug therapy within 6 months making longer term compliance an issue [5]. Third line therapies include Botulinum toxin (BT), PTNS, and SNS. BT can also be effective in up to 70% of cases; however, 39.8% of all who discontinued therapy, did so because of the side effects, including the risk of urinary retention [2]. The full effect of BT treatment is temporary and requires additional procedures every 4 to 9 months. PTNS is found to be around 55-70% effective, minimally invasive, and has very little side effects, but is temporary and requires frequent visit to the clinic (once a week) which may be difficult for patients who work full time or those who must travel a long distance to reach a provider [6] [7]. SNS is typically regarded as the most effective treatment at 85%, but it is also the most invasive[8]. SNS requires a surgical implant which may cause a series of adverse events. Further, the currently available neuromodulation options are open-loop and do not provide objective confirmation that the target nerve is being reached.

In summary, while there are many treatment options available to manage symptoms associated with OAB, each carry with it considerable drawbacks for patients. Patients drop out of the treatment pathway for OAB in great numbers. Further, of the 42 million adults in the United States estimated to have OAB, fewer than 500,000 have opted for neuromodulation treatment due to the need for surgery or temporary insertion as well as inconvenience, despite demonstrated clinical evidence.

There is a compelling clinical need for better treatment options that are not only effective and safe but also convenient, accessible, and have a minimal side effect profile. There is a need for a surgery-free and drug-free easy-to-use wearable system that allows patients to treat their chronic OAB symptoms when and where it is convenient for them and one that offers an objective confirmation that the neuromodulation target has been reached and one that automatically adjusts based on the patient's anatomy and movement during treatment sessions.

This study will evaluate the clinical efficacy, subject compliance, side-effects, and subject satisfaction of a surgery-free wearable and personalized bladder modulation system that provides personalized treatment through objective confirmation of nerve recruitment and can be used in the home by subjects suffering from the symptoms of OAB.

#### **4. Objectives**

- To compare the effectiveness of 1 treatment session per week to 3 treatment sessions per week on OAB symptoms using the Test Article.
- To evaluate the overall effectiveness
- To evaluate any side effects of the Test Article.
- To evaluate the tolerability, usability, and satisfaction of the Test Article.
- To evaluate the compliance by subjects using the Test Article.

#### **5. Study Design**

This is a prospective, multicenter study comparing the effectiveness of 1 treatment session per week to 3 treatment sessions per week using the Test Article on subjects diagnosed with OAB in a home environment.

After subjects have signed informed consent, they will undergo two screening evaluations. The first evaluation will involve examining the data collected during a 3-day bladder diary. The second evaluation will involve evaluation of the EMG signal produced while using the Test Article. Once the subject has met all eligibility and screening criteria, they will be enrolled in the study. Subjects will be randomized to once a week or three times a week of therapy. Demographic and baseline measurements will be taken including quality of life questionnaires and OAB questionnaires. All subjects will be given the Test Article and instructed on its use. All stimulation parameters will be personalized for the subject and within the commercially approved levels.

Subjects will be asked to use the Test Article either once (1) or three (3) times a week for thirty (30) minutes each time over a 12-week period. Subjects will either return to the clinic or have a remote visit (via phone/video conferencing) after one (1) week  $\pm$  2 days, four (4) weeks  $\pm$  4 days, eight (8) weeks  $\pm$  4 days, and twelve (12) weeks  $\pm$  4 days for evaluations. Subjects will be called by the site on the weeks they do not have a study visit and queried for any changes to health and medications, as well as address any questions or issues. If a subject needs additional training on use of any Test Article components, they will be asked to either return to the clinic or undergo troubleshooting

instructions over the phone. At the end of the twelve (12) weeks  $\pm$  4 days of stimulation treatments, eligible subjects will be offered the opportunity to participate in the long-term follow up portion of the study. Ineligible subjects and those that decline participation in the long-term portion will exit from the study and the Test Article will be collected by the site. Subjects electing to enroll in the follow up study will sign a new informed consent and then be instructed to taper down their treatment frequency stepwise from three treatment sessions per week, to two per week, to one per week, and finally one session every other week. The subjects that were assigned to one treatment session per week in the lead-in portion of the study will move directly to twice monthly treatment sessions. Subjects will then be instructed to perform treatments as needed or a minimum of twice per month.

### **5.1. Purpose**

The purpose of this study is to compare the efficacy, usability, safety, and comfort of 1 treatment session per week to 3 treatment sessions per week using the Test Article on subjects with OAB. This study will also help to evaluate the dose response of two different dose levels to aid in the development of a larger scale study to evaluate the safety and effectiveness of the Test Article.

### **5.2. Study Rationale**

Electrical stimulation has been used to treat chronic pain for several decades. This includes placing electrodes over the spinal cord, in deep brain structures, and over nerves in the periphery. Stimulation has also been used to treat disorders that are not pain related such as Parkinson's disease, epilepsy, and depression. Recently, SNS and PTNS have been used to modulate bladder function and treat subjects with OAB and provided some relief of OAB symptoms. However, currently commercial options for bladder modulation are invasive and have significant drawbacks that have limited their appeal to patients. SNS requires a major surgery, is costly and results in a permanent foreign body implant and, frequently, additional surgeries to replace batteries or address other issues PTNS requires a skin puncture and requires the Subject to travel to a physician's office weekly for therapy. Of the estimated 42 million adults in the United States with OAB, fewer than 500,000 are estimated to have been treated with commercially available neuromodulation options despite evidence of clinical efficacy.

The Test Article can be used in the home and offers personalized treatment through objective confirmation of nerve activation. It is noninvasive, eliminating the risk of surgery, and minimizes the inconvenience of frequent visits to the physician's office. This study will evaluate the tolerability, usability and satisfaction of the Test Article on subjects with OAB. Further, the study will also evaluate the use of evoked EMG signals to help control the Test Article and customize the stimulation experience for each subject.

## 6. Subject Selection

Selection Criteria	
Inclusion Criteria: To be eligible for study entry, subjects must satisfy all of the following inclusion criteria:
 

1. Male or female and 18 years of age or older at the time of enrollment

2. Willing and capable of giving informed consent

3. Willing and able to comply with study-related requirements and procedures

4. Are an appropriate candidate for the system required in this study based on the clinical judgment of the Investigator.

5. Have been diagnosed or have symptoms of OAB for at least 3 months prior to enrollment

6. Have an average of 10 or more frequency events per day in a 3-Day Bladder Diary

7. Able to provide clear, thoughtful responses to questions and questionnaires

8. Able to toilet self and have and maintain personal hygiene

9. Able to don and doff the bladder modulation garment on their ankle area, replace Gel Pads and use the controller

10. Have ankle and foot anatomy that allows the garment to fit properly, including having the hook and loop closures close and without excessive gapping and allowing the electrodes to fit firmly on the skin.

11. Able to sense and tolerate stimulation for the entire 30-minute therapy session

12. Has detectable EMG signal in response to modulation system stimulation during an investigator supervised screening session

13. If currently on medications that may affect their OAB symptoms, is on a stable dose (no new, discontinued, or change in dose) of all prescribed medication for at least 4 weeks prior to enrollment

14. Female subjects of child-bearing potential must have a negative urine dip stick pregnancy test at baseline

15. Have access to Wi-Fi at least weekly

16. Are capable of using the tablet-based controlling app

---------------------------	--

**Exclusion Criteria:** Subjects will be excluded from the study if 1 or more of the following exclusion criteria are applicable:

1. Have evidence of an active disruptive psychological or psychiatric disorder or other known condition significant enough to impact perception of pain, compliance of intervention and/or ability to evaluate treatment outcomes, in the opinion of the investigator.
2. Allergic, or have shown hypersensitivity, to any materials of the system which come into contact with the body.
3. Have a pacemaker or implanted defibrillator.
4. Have a documented current or reoccurring Urinary Tract Infection (3 or more in the 12 months prior to enrollment).
5. Current use of a marketed device for treatment of their OAB or incontinence (including but not limited to Interstim®).
6. Have had botulinum toxin treatment for their OAB in the previous 8 months.
7. Current use of TENS in pelvic region, back or legs.
8. Had PTNS treatment within 6 months prior to enrollment.
9. Use of investigational drug/device therapy within past 12 weeks.
10. Current participation in another clinical study.
11. Had within 6 months of enrollment a significant untreated substance abuse disorder or polysubstance abuse disorder stemming from dependency-producing medications, alcohol, and/or illicit drugs.
12. Pregnant or planning to become pregnant within the next 12 weeks.
13. Has scar tissue, metal, or other implant in the target ankle that would interfere with stimulation.
14. Has a neurological disorder that causes abnormal sensations in the lower leg (loss of sensation or allodynia).
15. Has a neurological disorder that affects the bladder or a diagnosis of interstitial cystitis, radiation cystitis, or fistulas.
16. Has a skin condition in the area of the ankle stimulation location that would preclude them from using surface stimulation.
17. Has been diagnosed with incontinence due to neurogenic bladder.
18. Have failed a third line treatment for their OAB because of lack of effectiveness in the last 2 years (PTNS, botulinum toxin, or SNS).
19. Urge incontinence due to stress-predominant mixed urinary incontinence (greater than 60% of the time)
20. Have polyuria (>2500 cc urine output per day)
21. Has urinary retention or incomplete bladder emptying
22. Has symptoms of benign prostatic hyperplasia (BPH) - weak stream, straining, hesitancy or intermittency.

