## 7.12. Visit Schedule for Lead-in Phase

## 8. Long-Term Follow-Up Phase

### 8.1. Subject Selection

Selection Criteria	
Inclusion Criteria: To be eligible for entry into the long-term follow-up portion of the study, subjects must satisfy all the following inclusion criteria:
 

1. Successful completion of the lead-in portion of the FREEOAB study

2. A rating of 5 or greater on the PGIC questionnaire at Visit 5

3. A minimum compliance of 90% with diary and questionnaire completion

4. A minimum compliance of 80% with stimulation sessions during the lead-in portion of the FREEOAB study.

 
Exclusion Criteria: Subjects will be excluded from participation if the following exclusion criteria are met:
 

1. Any change in health status that might affect the subject's ability to comply with the visit schedule, assessments, and/or stimulation session completion.

---------------------------	--

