## 8.11. Visit Schedule for Long-Term Follow-Up Phase

	Visit 6	Visit 7	Visit 8	Visit 9	Visit 10	Visit 11
Study Phase	enrollment	Month 6	Month 9	Month 12	Month 18	Month 24
Informed Consent	X					
3-day Bladder Diary (a,b)	X	X	X	X	X	X
Inclusion/Exclusion Check	X					
OAB-q				X		X
IIQ-7				X		X
I-QoL				X		X
PGIC		X	X	X	X	X
OHQ				X		X
Study Visit Form	X	X	X	X	X	X
Exit Form						X

a - 3-Day Bladder Diary to be dispensed at Visit 6, Visit 7, Visit 8, Visit 9, and Visit 10.

b - 3-Day Bladder Diary to be collected at Visit 7, Visit 8, Visit 9, Visit 10, and Visit 11.

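### The lead-in bars pregnancy at entry, but the long-term phase continues home stimulation for 21 months with no explicit pregnancy criterion, question or stopping rule

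*Combined protocol and SAP*

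**What the plan says.** **Lead-in.** Section 6, Inclusion 14: "Female subjects of child-bearing potential must have a negative urine dip stick pregnancy test at baseline". Exclusion 12: "Pregnant or planning to become pregnant within the next 12 weeks". The look-ahead equals the length of the lead-in.

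**Duration.** Section 2 (Structure) describes a "12-week treatment duration with an optional additional 21-month long-term follow-up period, for a total participation time of 24 months". On sessions after the taper, Section 5 says: "Subjects will then be instructed to perform treatments as needed or a minimum of twice per month".

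**Long-term entry.** Section 8.1 opens: "To be eligible for entry into the long-term follow-up portion of the study, subjects must satisfy all the following inclusion criteria". Four inclusions follow: lead-in completion, a PGIC rating of at least 5, diary and questionnaire compliance of at least 90%, and session compliance of at least 80%. The single exclusion is a change in health that might affect the subject's "ability to comply with the visit schedule, assessments, and/or stimulation session completion". Pregnancy is not mentioned.

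**Long-term conduct.** Sections 8.4 to 8.9 list consent, the new treatment schedule, diaries, questionnaires and, from Visit 7, a query about adverse events and medication. The table in 8.11 has a row "Inclusion/Exclusion Check" at Visit 6 and no row for a pregnancy test.

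**Stopping and safety.** Section 14 gives an open list of discontinuation reasons that does not name pregnancy. Section 12.1 counts fetal distress, fetal death and birth defects as serious adverse events, and 12.3 requires adverse events to be reported up to study exit.

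**The concern.** The sponsor chose to keep pregnant women out of the 12-week treatment period. The same device is then used at home for a much longer period, and the safeguard is not restated there. Exclusion 12 by its own terms admits a woman who plans to conceive in, say, month 4, and she may later enter the long-term phase. No reason is given for treating the two periods differently.

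The amendment summary in Section 21 fits an oversight: Version 2 added Section 8, and Section 6 is not among the sections listed as changed. That is consistent with a criterion not carried forward, but does not prove it.

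What is at stake is participant protection and the completeness of the safety data. Section 11 says the device is not approved for sale anywhere, and 17.1 says it has had no animal testing. In the long-term phase, nothing in the visible plan actively identifies a pregnancy or says what happens to stimulation when one is reported.

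**Working it through.** **1. The plan's duration.** 12 weeks × 7 / 30.4375 = 2.76 months, and 2.76 + 21 = 23.76 months. This reproduces the stated total of 24 months.

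**2. The two phases side by side.**

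| | Lead-in | Long-term phase |
|---|---|---|
| Entry criterion | Inclusion 14, Exclusion 12 | None explicit; health-change exclusion in 8.1 |
| Test | Baseline dipstick | None in 8.4 to 8.9 or 8.11 |
| Contact | Weekly visit or call (7.2) | Months 6, 9, 12, 18 and 24; no calls listed (8.3) |
| Visits that must be in clinic after the phase's entry visit | Visit 5 | Visit 11 |
| Specific rule if pregnancy begins | None in Section 14 | None in Section 14 |

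**3. Does the Visit 6 eligibility check bring Section 6 back?** Not sensibly. Exclusion 9 of that list is "Use of investigational drug/device therapy within past 12 weeks". Applied at Visit 6, it would remove every subject who had just finished the lead-in on this investigational device. The check must therefore mean the list in 8.1.

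**4. Share of participation.** 21 / 24 = 87.5% of the maximum participation time falls in the long-term phase.

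**5. Share of sessions.** Inputs: two sessions a month as the stated minimum (Section 5); one or three a week for 12 weeks in the lead-in.
- Long-term minimum: 21 × 2 = 42.
- Lead-in: 12 × 1 = 12, or 12 × 3 = 36.
- Once-weekly arm: 42 / (42 + 12) = 77.8%.
- Three-times-weekly arm: 42 / (42 + 36) = 53.8%.

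Both shares are lower bounds for a subject who completes every lead-in session and stays to month 24. As-needed sessions come on top, as do taper sessions in the three-times-weekly arm (taper length is not given).

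**6. Longest gap between visits.** Visits at months 3, 6, 9, 12, 18 and 24 leave gaps of 3, 3, 3, 6 and 6 months. In a six-month gap, 6 × 2 = 12 sessions is the minimum.

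**7. Number affected.** The documents do not give the number of women of child-bearing potential. Entry requires lead-in completion, so the number lies between 0 and about 80, the planned completers. The entry thresholds and optional enrolment pull it down further.

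**The case against.** The case on the other side is substantial, and it limits the point.

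- **The health-change exclusion looks forward.** It covers a change that might affect compliance over the following 21 months. A woman pregnant at Visit 6 would be expected to deliver in that time, so an investigator could naturally exclude her. A reader might infer that the plan admits any pregnant woman who can still attend. The text does not support that. It supports only that her exclusion rests on judgement.
- **A single test cannot be confirmed.** The lead-in schedule table (7.12) is not visible. A Week 12 test could stand there, and Visits 5 and 6 may share a day. Visit steps are also weak evidence of absence: the mandatory baseline dipstick is missing from the Visit 0 and Visit 1 steps. Likewise, 8.11 has no adverse-event row although Visits 7 to 11 require that query.
- **Fetal events are reportable.** Adverse events are queried at Visits 7 to 11, and serious ones must be reported within 24 hours. To say that such events would be missed goes too far. The residual gap is active identification, and follow-up of a pregnancy that continues past exit.
- **Nothing forces a pregnant subject to continue.** The list in Section 14 is open and includes voluntary withdrawal.
- **No fetal hazard is shown.** The plan never says why pregnancy is excluded; 17.1 names skin irritation as the main risk and calls risks minimal. A reader might infer danger to a fetus from the exclusion, but the documents give no basis for that.
- **The long-term consent form is not visible** and may carry pregnancy instructions.

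All of these stand as limits. None of the visible provisions identifies a pregnancy that starts during the phase or tells anyone to stop stimulation when it is found.

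**Conclusion.** The point holds as a gap in explicit wording. Read as it stands, the visible plan protects less in the long-term phase than the sponsor's own lead-in rule does. Pregnancy at Visit 6 is left to discretion, and a later pregnancy has no stated handling beyond general reporting and discretionary withdrawal.

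The 87.5% of time and the minimum of 42 sessions describe how much exposure lies outside an explicit rule. They assume full 24-month participation and say nothing about risk. The conclusion assumes that neither the 7.12 table nor the long-term consent form supplies the missing safeguard; if either does, the point shrinks to aligning the protocol text. It is a low-cost improvement to participant protection and safety data, with no bearing on the efficacy comparison.

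**What to change.** 1. **8.1:** add pregnancy at Visit 6 as an explicit exclusion. Confirm by urine dipstick in women of child-bearing potential before the new treatment schedule is given, unless already tested at Visit 5. Show this in 8.4 and 8.11.
2. **8.5 to 8.9:** ask about pregnancy with the adverse-event query at Visits 7 to 11.
3. **8.4:** tell subjects to report a pregnancy between visits.
4. **Section 14:** state that stimulation stops on confirmed pregnancy and that the pregnancy is followed to outcome.

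An exclusion for planning pregnancy over 21 months is not needed if these are in place. If the sponsor considers pregnancy acceptable in this phase, a sentence saying so, with the reason, would settle the matter.

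**Cost:** at most one dipstick per eligible woman at a clinic visit already scheduled, one question at each of five existing visits, and a wording amendment. No visits are added. A few long-term subjects may be lost.
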